### **Efficacy Measures**

10. CMV Infection (Secondary Outcome) – defined as detectable CMV in the patient's plasma. Currently, MUSC uses CMV DNA PCR (plasma IU/mL) to assess for infection with nucleic acid amplification techniques that are calibrated to the WHO international standard for human CMV. The lower level of detection is 50 IU/mL. Per the MUSC CMV protocol and usual care (see Appendix), any level >1,000 IU/mL will be considered CMV infection for the purposes of this study. All cases of CMV infection, regardless of the presence or absence of symptoms, will be classified as infection. CMV DNA PCR is measured at MUSC per our protocol using event-driven criteria, which includes either leukopenia or symptoms consistent with CMV infection (N/V/D, anorexia, fever, chills, and/or malaise). For the purposes of this study, the reason for measuring CMV DNA PCR will be captured and analyzed as well. Further, MUSC usual care CMV protocol suggests measuring CMV DNA PCR in those that are D+/R- after prophylaxis is discontinued (post-transplant month 7, 9 and 12). The protocol also recommends measuring CMV DNA PCR at month 4, 7, and 12 after discontinuation of antiviral prophylaxis in moderate risk patients (R+, see Appendix). CMV symptoms and treatment will also be recorded. Late CMV infection will be defined based on occurrence of first CMV infection after completion of CMV prophylaxis (3- or 6-months post-transplant). These endpoints will be assessed at 3-, 6-, and 12-months post-transplant. Breakthrough cases of CMV infection, defined as the presence of CMV DNA while on anti-CMV prophylaxis, will also be assessed.
11. CMV Disease (Secondary Outcome) – defined as the presence of organ dysfunction in the setting of CMV infection with biopsy proven presence of CMV in the affected organ, done at MUSC using DNA hybridization. This will be sub-classified by organ type; most common in kidney transplant recipients will be CMV gastrointestinal disease, CMV pneumonia, or CMV nephritis. Less common include CMV hepatitis, CMV retinitis, CMV encephalitis, CMV cystitis, CMV myocarditis, and CMV pancreatitis. Late CMV disease will be defined based on occurrence of first CMV infection after completion of CMV prophylaxis (3- or 6-months post-transplant). This endpoint will be assessed at 3-, 6-, and 12-months post-transplant. Breakthrough cases of CMV disease will also be assessed.
12. Probable or Likely Refractory CMV Infection (Exploratory Outcome) – defined as a persistent viral load (CMV viral load at the same level or higher than the peak viral load within 1 week but <1 log 10 increase in CMV DNA titers done in the same laboratory and with the same assay) after at least 2 weeks of appropriately dosed anti-viral therapy.

13. CMV Antiviral Drug Resistance (Exploratory Outcome) – defined as a viral genetic alteration that decreases susceptibility to one or more antiviral drugs. This is a send out laboratory assessment at MUSC. All send out reports for patients in this study will be reviewed for possibility of resistance. We will capture and report the type of resistance in terms of the specific mutations and which agents are likely to incur resistance based on these gene variants.

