## 1.0 Objectives / Specific Aims

- Aim 1. Assess the incidence of leukopenia in those randomized to maribavir vs. valganciclovir prophylaxis in adult kidney transplant recipients at high-risk of CMV infection.
  - Hypothesis 1. The incidence of clinically meaningful leukopenia, defined as a WBC count of  $< 3,000$  cells/mm^3 and a reduction in total mycophenolate dose below 1,500 mg/day or valganciclovir dose below 900mg per day (adjusted for renal function), will be significantly lower in the maribavir arm, as compared to the valganciclovir arm.
- Aim 2. Assess the efficacy of maribavir vs. valganciclovir prophylaxis in adult kidney transplant recipients at high-risk of CMV infection.
  - Hypothesis 2. The incidence of CMV infection and disease will be similar between the maribavir arm, as compared to the valganciclovir arm, at 3-, 6-, and 12-months post-transplant.
- Aim 3. Assess the impact of maribavir vs. valganciclovir prophylaxis on healthcare utilization and costs in adult kidney transplant recipients at high-risk of CMV infection.
  - Hypothesis 3. Healthcare utilization will be lower in the maribavir arm, as compared to the valganciclovir arm, at 6- and 12-months post-transplant, driven predominantly by reduced number of telephone calls, televisits, and laboratory monitoring encounters.
- Exploratory Aim 4. Assess the impact of maribavir vs. valganciclovir prophylaxis in adult kidney transplant recipients at high-risk of CMV infection on patient-reported outcomes for quality of life and satisfaction.
- Exploratory Aim 5. Assess any differences in leukopenia, efficacy, healthcare utilization and patient reported outcomes by race and sex in patients randomized to maribavir vs. valganciclovir prophylaxis in adult kidney transplant recipients at high-risk of CMV infection.

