### 3.0 Intervention

Patients will be randomized to receive either maribavir 400mg PO BID or valganciclovir 900mg daily (standard of care dose, adjusted for renal function) for CMV prophylaxis for 3 to 6 months post-transplant. Those that are CMV serostatus D+/R- will receive 6 months of antiviral therapy; all others will receive 3-months of therapy. The current gold-standard therapy is valganciclovir for 3- to 6-months of therapy. Those randomized to maribavir will also receive 1-month of acyclovir 400mg PO BID for HSV prophylaxis (standard of care dose). Beyond these interventions, all follow-up care and laboratory monitoring will be conducted as per usual care protocols. All immunosuppression will be given and dosed as per usual care protocols. There will be no additional visits or laboratory measurements as part of this study.

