Data collection will be as follows: Baseline data will include sociodemographics, comorbidities, serologies, donor information and transplant characteristics. Follow-up data will include induction therapy, immunosuppression type, dosing and levels, laboratory data, biopsy pathology reports, infection type and severity, hospitalizations and cause, ED visits and cause, allograft function, graft loss and death. All data will be gathered in a comprehensive manner using both electronic and manual chart abstraction. There are no study-specific procedures that will be conducted. All follow-up data that is accessible in the MUSC electronic medical record (EMR) will be gathered, curated, aggregated, and analyzed. Both MUSC and external non-MUSC labs are entered into the EMR. All acute rejections are confirmed by biopsy and pathology reports available in the EMR. All graft loss and death events are also documented in the EMR. Clinically significant infections, particularly CMV, are also well-documented in the MUSC EMR. Hospitalizations and ED visit within MUSC will be captured; however, non-MUSC outside hospitalizations and ED visits will not be accessible for this study. Below is a table outlining key follow-up time periods and data elements collected during these times.

Assessments		Pre-transplant	Day Post-transplant							Week Post-Txp		Month Post-transplant		
Time Frame			1	2	3	4	5	6	7	2	4	3	6	12
RANDOMIZATION			X											
History and Physical 		X							X		X	X	X	X
Vital Signs		X	X			X			X	X	X	X	X	X
Serologies 		X												
Laboratory Assessment	CBC and BMP	X	X			X			X	X	X	X	X	X
	Tacrolimus levels				X				X	X	X	X	X	X
CMV Infection Assessment									X		X	X	X	X
Clinical assessment 									X	X	X	X	X	X
HRQOL PROMIS Survey												X	X	X
QualityMetric Patient Satisfaction Survey												X	X	X

Foot notes:

1. Within 48 hours of transplant
2. Includes testing for CMV, Epstein-Barr, hepatitis B & C and HIV for donor and recipients
3. Includes assessments of adverse events, antiviral drug doses, allograft rejection, infection, need for dialysis, hospitalization, ED visits, graft loss, and all immunosuppressant medications and doses

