### **Power/Sample Size**

This study is adequately powered to detect a clinically meaningful and statistically significant difference in the incidence of clinically significant leukopenia in those randomized to maribavir vs. valganciclovir under most incident rate scenarios. For this study, clinically significant leukopenia is defined as a WBC count of <3,000 AND a reduction in the dose of mycophenolate or valganciclovir dose. Based on a retrospective analysis of internal data, the expected incidence of clinically significant leukopenia in the valganciclovir arm is between 33 and 35%. To support this incident rate, we conducted a retrospective analysis of our internal data to fully assess the incidence of clinically significant leukopenia. In this analysis, we included 446 adult kidney transplant recipients transplanted at MUSC between 2007 and 2015. We chose this time period as we had comprehensive data on induction, WBC counts, and MMF dosing to allow for assessment of the incidence of clinically significant leukopenia. Of these patients, 127 (28%) received rATG induction. The incidence of WBC <3K with and without MMF dose reduction is detailed in the table below, which was assessed within 1 year of transplant. This data matches our expected incidence of leukopenia in the VGC arm of 35%. This is because patients in the proposed study will be receiving rATG or be CMV D+/R- and receive 6-months of VCG/maribavir and be at higher risk of leukopenia.

[figure not shown]
Induction Agent	N	WBC <3K	WBC <3K and MMF Dose Reduction
Basiliximab	319	36.7%	21.3%
rATG	127	56.7%	34.6%

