The incidence of clinically significant leukopenia (WBC <3K AND dose reduction in MMF) is difficult to assess in the maribavir arm, as this specific issue is not reported in the published data. However, there are several studies that can be used to estimate this incidence for power/sample size purposes. In a study conducted in liver transplant patients, known to be at higher risk for cytopenias than kidney recipients, the incidence of neutropenia was 6% in the maribavir arm (Winston DJ et al Am J Transplant 2012;12:3021-30.). In a phase III prophylaxis study in allogeneic stem-cell transplants, who are very high risk for cytopenias, the incidence of neutropenia was similar between the maribavir, and placebo arms and the average WBC count was 4.2K in the placebo arm and 4.4K in the maribavir arm (Papanicolaou GA et al. Clin Inf Diseases 2019;68:1255-64.). Thus, maribavir does not appear to induce or worsen leukopenia and a 5% incidence is a reasonable expectation in the maribavir treatment arm for estimating sample size and power.

To meet at least 80% power, given an incident rate of 33 to 35% in the valganciclovir arm and 5 to 6% in the maribavir arm, 32 patients in each arm is required, assuming two independent samples, a two sided  $\alpha=0.05$ , and using the chi square test. This sample-size will be inflated to 35 patients per arm to address an expected dropout/lost to follow-up rate of 3-5% in each arm. Thus, 70 total patients, 35 in each arm, will provide adequate power to assess the primary aim of this study. SAS 9.4 (SAS Institute, Cary, NC) was utilized to conduct sample-size estimations (Proc Power).

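### Leukopenia is one of the triggers for CMV PCR, so CMV infection during prophylaxis is likely to be under-detected with maribavir, by an uncertain amount, and no analysis is specified to show it

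*Combined protocol and SAP*

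**What the plan says.** Section 4.0, Efficacy Measures, item 10 describes how CMV infection is found: "CMV DNA PCR is measured at MUSC per our protocol using event-driven criteria, which includes either leukopenia or symptoms consistent with CMV infection". Any level above 1,000 IU/mL counts, with or without symptoms. Breakthrough infection is CMV DNA found while the patient is on prophylaxis. Usual care suggests PCR at months 7, 9 and 12 in D+/R- patients and recommends it at months 4, 7 and 12 in R+ patients, in both cases after prophylaxis has stopped. Item 10 adds that "the reason for measuring CMV DNA PCR will be captured and analyzed as well".

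Section 3.0 sets prophylaxis at 6 months for D+/R- patients and 3 months for all others, and states: "There will be no additional visits or laboratory measurements as part of this study".

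Section 1.0 predicts that clinically meaningful leukopenia "will be significantly lower in the maribavir arm, as compared to the valganciclovir arm". For efficacy it predicts: "The incidence of CMV infection and disease will be similar between the maribavir arm, as compared to the valganciclovir arm", at 3, 6 and 12 months. No margin is given.

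The Power/Sample Size section plans for 80% power "given an incident rate of 33 to 35% in the valganciclovir arm and 5 to 6% in the maribavir arm".

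The schedule in Section 10.0 has a row "CMV Infection Assessment", marked at day 7, week 4 and months 3, 6 and 12.

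**The concern.** Whether an asymptomatic infection is counted depends on whether someone orders a PCR. One of the two named reasons for ordering it is the outcome that treatment is expected to change. If maribavir causes less leukopenia, maribavir patients are tested less often, and silent viremia during prophylaxis is found less often in that arm even if it is equally common.

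The direction matters because Aim 2 hopes to see similar rates and sets no margin, so missed maribavir cases support the hoped-for conclusion. The plan also expects unequal laboratory activity: the Background says leukopenia on valganciclovir leads to further testing, and Hypothesis 3 predicts fewer laboratory encounters with maribavir.

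Timing can be distorted too. Late infection is defined by a first infection after prophylaxis ends, so a breakthrough infection that was missed and persists to the first post-prophylaxis PCR would be classed as late.

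The Statistical Methods compare CMV infection by chi-square, Fisher's exact test or Cox regression and do not use the reason for PCR.

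**Working it through.** **The plan's own figure.** The documents give no figure for CMV detection. The leukopenia rates that drive this point are those used for sample size, so I checked that calculation. For 33% versus 6% with 64 patients, the likelihood-ratio chi-square formula uses the mean rate 0.195 and a noncentrality of 64 × Σ[p ln(p/0.195) + (1−p) ln((1−p)/0.805)], summed over the two arms. This is 64 × 0.1256 = 8.04. Power is Φ(√8.04 − 1.96) = Φ(0.876) = 0.809, which matches the plan's table (N = 64, power 0.809). At 35% and 5%, the expected counts are 0.35 × 35 ≈ 12 valganciclovir patients and 0.05 × 35 ≈ 2 maribavir patients.

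**Where scheduled PCR is absent from the text**

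| Comparison | Scheduled PCR named in item 10 |
|---|---|
| Breakthrough infection | None |
| 3 months, all patients | None |
| 6 months, D+/R- | None (first at month 7) |
| 6 months, R+ | Month 4 |
| 12 months, D+/R- and R+ | Yes, as suggested or recommended usual care |
| D-/R- patients enrolled through rATG | No schedule named |

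**Illustrative model.** The probability that an infection is detected is D = 1 − (1−s)(1−L)(1−c), where:
- s is the share of infections whose symptoms prompt a PCR (assumed 0.25, 0.50, 0.75);
- L is the probability of leukopenia-prompted testing (35% valganciclovir, 5% maribavir, from the Power section);
- c is the share caught by scheduled PCR (assumed 0, 0.5, 0.9).

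Triggers are taken as independent and true infection rates as equal. The apparent ratio is D(maribavir)/D(valganciclovir).

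| s | c = 0 | c = 0.5 | c = 0.9 |
|---|---|---|---|
| 0.25 | 0.2875/0.5125 = 0.56 | 0.85 | 0.98 |
| 0.50 | 0.525/0.675 = 0.78 | 0.91 | 0.98 |
| 0.75 | 0.7625/0.8375 = 0.91 | 0.96 | 0.99 |

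At s = 0.50 and c = 0, a true excess of 1/0.778 = 1.29-fold on maribavir would look like equality.

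**CMV as a cause of leukopenia.** If half of infections themselves cause leukopenia in either arm, the factor (1−c) is replaced by 0.5 and the ratios are 0.85, 0.91 and 0.96.

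**Counts.** With c = 0, the difference in detection is 0.225 at s = 0.25 and 0.075 at s = 0.75. The Background cites early infection of 6%, or 0.06 × 35 = 2.1 true cases per arm, so 0.2 to 0.5 fewer cases would be detected on maribavir. At the late rate of 17% (5.95 cases) the shortfall would be 0.4 to 1.3, if no scheduled PCR were done.

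**Like-for-like trigger.** The power text says "The incidence of WBC <3K with and without MMF dose reduction is detailed in the table below": 56.7% with and without dose reduction combined (any WBC below 3,000) and 34.6% with dose reduction, in rATG recipients. If any WBC below 3,000 is the trigger and the basiliximab figure of 36.7% stands in for maribavir (an assumption), the ratios at c = 0 are 0.525/0.675 = 0.78, 0.6835/0.7835 = 0.87 and 0.842/0.892 = 0.94.

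**The case against.** The other side has several good points.

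- Item 10 says the criteria include leukopenia and symptoms; it does not say these are the only triggers. It refers to an Appendix that is not in the text I have. Other testing during prophylaxis cannot be ruled out.
- The 35% and 5% describe leukopenia with a dose reduction, whereas the trigger as stated has no such condition. The 5% is inferred from neutropenia and white-count data in liver and stem-cell recipients. The internal rates are one-year incidences, while prophylaxis lasts 3 or 6 months, and leukopenia outside the viremic period detects nothing.
- The Background names breakthrough CMV and mycophenolate as causes of a low white count. Both act in either arm, so independence is doubtful and the bias shrinks.
- Symptoms prompt testing in both arms, and post-prophylaxis PCR does not depend on arm. In an open-label trial clinicians might test either arm more.
- CMV infection is a secondary outcome, the plan admits limited power for it, and the absolute counts are small.

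All of this limits the size and certainty of the bias. It does not remove the mechanism or its likely direction, and a caveat about power does not disclose a bias.

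A reader might also infer that infections found through leukopenia should be dropped from the main count. That does not follow. They are genuine infections, and those caught early and treated may never become symptomatic, so removing them can reverse the bias. If half of such detections pre-empt symptoms (an assumption), the ratio becomes (1 − 0.5 × 0.05)/(1 − 0.5 × 0.35) = 0.975/0.825 = 1.18; if all do, 0.95/0.65 = 1.46.

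**Conclusion.** As written, the plan gives a CMV infection comparison with differential ascertainment, likely to favour maribavir and the hypothesis of similar efficacy. It matters most for breakthrough infection, the 3-month comparison and the 6-month comparison in D+/R- patients. A plausible apparent ratio under equal true rates is 0.56–0.91 without scheduled PCR, 0.85–0.96 if half of infections cause leukopenia, and 0.85–0.99 where scheduled PCR catches half to nine-tenths of infections. These rest on assumed s and c and on leukopenia rates that are not those of the trigger itself, so the true gap could be larger or smaller.

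Three stronger readings are not supported:

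- That the whole endpoint is certain to be biased. The 12-month result is partly protected by post-prophylaxis PCR, and the trigger list may not be complete.
- That the bias is as large as 0.43 or 0.67. Those values (s = 0.25 and 0.50) pair 56.7% for any low white count with 5% for low count plus dose reduction, which are different events. At 35% versus 5%, a true doubling would still appear as 1.12 to 1.82 (2 × 0.56 to 2 × 0.91).
- That the schedule contradicts item 10. The CMV row is separate from the laboratory rows and is not stated to be a PCR. It is unclear, not shown to be inconsistent.

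**What to change.** 1. Keep every PCR-confirmed infection above 1,000 IU/mL in the main analysis.
2. Using the reason for PCR that is already captured, pre-specify a sensitivity analysis that excludes infections found only through a leukopenia-prompted PCR, and report those infections separately by arm.
3. Report PCRs per patient-month by arm, by reason, and on versus off prophylaxis.
4. State in advance that a finding of similar CMV infection during prophylaxis will be read in light of both analyses.
5. Say whether the CMV row of the Section 10.0 schedule is a PCR, and reconcile it with item 10.

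The cost is a little analysis work and no extra test. The sensitivity analysis may lean the other way, for the reason given under the objection, so it should stand beside the main result and not replace it. It should be fixed before the data are seen; chosen afterwards, it would carry little weight.

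### No scheduled CMV PCR is described during prophylaxis, so an on-drug infection that prompts no test is either labeled late or missed

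*Combined protocol and SAP*

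**What the plan says.** Section 3.0 sets the length of prophylaxis: "Those that are CMV serostatus D+/R- will receive 6 months of antiviral therapy; all others will receive 3-months of therapy".

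Section 4.0, item 10, describes two kinds of testing.

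- Prompted: "CMV DNA PCR is measured at MUSC per our protocol using event-driven criteria, which includes either leukopenia or symptoms consistent with CMV infection".
- Scheduled, for D+/R-: the center's usual-care protocol "suggests measuring CMV DNA PCR in those that are D+/R- after prophylaxis is discontinued (post-transplant month 7, 9 and 12").
- Scheduled, for R+: "The protocol also recommends measuring CMV DNA PCR at month 4, 7, and 12 after discontinuation of antiviral prophylaxis in moderate risk patients".

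D-/R- recipients can enter under section 5.0 if they received rATG, but item 10 lists no scheduled PCR for them.

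Item 10 sets the study threshold for infection above 1,000 IU/mL, counts infection whether or not there are symptoms, and reports it at 3, 6 and 12 months. It reports breakthrough cases (CMV DNA found during prophylaxis) separately from late ones: "Late CMV infection will be defined based on occurrence of first CMV infection after completion of CMV prophylaxis". The reason for each PCR is to be recorded and analyzed. In item 11, late CMV disease is likewise keyed to the first CMV infection.

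The assessment table in section 10.0 has a row "CMV Infection Assessment", marked at day 7, week 4 and months 3, 6 and 12. No footnote says what the assessment consists of. Section 3.0 says the study adds no laboratory tests to usual care.

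**The concern.** Silent infection is part of the endpoint, but the testing described can find it during prophylaxis only if leukopenia happens to prompt a PCR. The late label then rests on when the infection was detected, with nothing to show that it began after the drug was stopped.

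Breakthrough infection is the direct measure of whether a prophylactic drug works while it is being taken, and here it is the quantity that loses cases. Hypothesis 2 expects similar CMV incidence at 3, 6 and 12 months. A low count at month 3 may partly reflect that no scheduled test has yet been done. The optional Cox models for Aim 2 (section 10.0, Statistical Methods) give no rule for dating such infections; if they are dated at detection, they will cluster at the scheduled test months.

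**Working it through.** **Step 1. Count the scheduled PCRs.** The inputs are the courses in section 3.0 and the test months in item 10. The R+ sentence does not say clearly whether its months run from transplant or from drug stop, so both readings are shown. From drug stop after a 3-month course, the tests fall at 3+4 = 7, 3+7 = 10 and 3+12 = 15 months after transplant.

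| Group | Course (months) | Scheduled PCR (months after transplant) | During course | By month 3 / 6 / 12 |
|---|---|---|---|---|
| D+/R- | 6 | 7, 9, 12 | 0 | 0 / 0 / 3 |
| R+, counted from transplant | 3 | 4, 7, 12 | 0 | 0 / 1 / 3 |
| R+, counted from drug stop | 3 | 7, 10, 15 | 0 | 0 / 0 / 2 |
| D-/R- with rATG | 3 | none listed | 0 | none listed |

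Under every reading, no scheduled PCR falls within the course.

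**Step 2. Follow the rule for silent viremia that starts on drug.** Let *q* be its true rate, *e* the chance that a PCR is prompted while it is present, and *s* the share of unprompted cases still above threshold at the first PCR after prophylaxis.

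- Counted as breakthrough: *q* × *e*
- Labeled late: *q* × (1 − *e*) × *s*
- Missed: *q* × (1 − *e*) × (1 − *s*)

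The shortfall in breakthrough is *q* × (1 − *e*), whatever the value of *s*. The excess in late infection depends on *s*.

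**Step 3. See whether the documents fix the size.** They give none of *q*, *e* or *s*, so the values below are assumptions. For *q* the stand-in is the early infection rate on prophylaxis from the systematic review in the Background, 6% (95% CI 1 to 31%). That is a rate of early infection in general and does not isolate silent viremia. For *e* the range is 5% (the planning rate of leukopenia on maribavir) to 56.7% (WBC below 3,000 among rATG patients in the internal data). These mark the ends of a range and do not compare the arms. For *s* the range is 0.25 to 1.

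- *q* = 6%, *s* = 1, *e* = 5%: breakthrough 0.06 × 0.05 = 0.3%; labeled late 0.06 × 0.95 = 5.7%, or 2.0 of 35 patients.
- *q* = 6%, *s* = 1, *e* = 56.7%: breakthrough 0.06 × 0.567 = 3.4%; labeled late 0.06 × 0.433 = 2.6%, or 0.9 of 35.
- *q* = 6%, *s* = 0.25: labeled late falls to 1.4% (*e* = 5%) or 0.6% (*e* = 56.7%), and the rest of the unprompted cases are missed.
- *q* from 1% to 31%, *s* = 1: labeled late runs from 0.01 × 0.433 = 0.4% to 0.31 × 0.95 = 29%.

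The range is too wide to serve as an estimate. The direction for breakthrough is fixed as long as some silent cases go untested.

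**Step 4. Set the table row beside the text.** If the CMV row meant PCR, every patient would have 3, 4 and 5 scheduled tests by months 3, 6 and 12. Its times share only month 12 with item 10, and for R+ patients counted from drug stop they share none. The row is separate from the laboratory rows and does not name PCR. Together with the statement in section 3.0, this makes review of the record the more natural reading, but the table does not say so.

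**The case against.** **The calendar is the same in both arms, and the planned tests compare arms.** This stands. A reader might infer that the scheduled calendar itself biases the comparison of arms at 3, 6 or 12 months; the documents do not support that. Whether the leukopenia trigger leads to more testing in one arm is a separate question.

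**The reason for each PCR is captured.** This is a real mitigation. It separates scheduled from triggered detections, but it does not recover the time of onset, and no rule links it to the breakthrough or late label.

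**The table does not truly contradict the text.** Largely right. A reader might infer that two rival PCR schedules exist, but section 3.0 argues against that. What remains is an undefined row.

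**Month 12 evens things out.** A reader might infer that by then every group has had three routine tests. That fails for R+ patients if the months run from drug stop and for D-/R- patients, and the tests are only suggested or recommended. Nor can every month-6 detection be called triggered, since R+ patients may have had one scheduled PCR by then.

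**The look-back is mostly on-drug time.** The on-drug share of the interval before the first scheduled PCR is 6/7 = 86% for D+/R- patients and 3/4 = 75% or 3/7 = 43% for R+ patients. These are shares of calendar time. They ignore prompted tests and say nothing about the share of infections misplaced.

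**CMV infection is a secondary outcome with admitted low power.** True, and this limits the priority. Low power is a matter of precision, however, and does not answer a rule that puts cases in the wrong category.

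Item 10 also refers to an Appendix holding the center's CMV protocol. It is not in the text supplied for review and may settle where the R+ months start.

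**Conclusion.** The concern holds for the breakthrough/late split and for the time pattern of CMV infection. Applied as written, the rule labels as late any silent on-drug infection that prompts no test and persists above threshold to the first PCR after prophylaxis; those that clear are lost. Late CMV disease inherits the label, though biopsy-proven organ disease is less likely to begin silently.

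The size is unknown. The conclusion assumes that some on-drug viremia occurs without a prompted test, that item 10 describes all the scheduled testing, and that the table row is not a PCR. If the row does mean PCR, on-drug infections could be found at those visits and the problem would shrink. The point is a correction worth making before analysis and does not affect the primary outcome.

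**What to change.** 1. In items 10 and 11, classify a first positive at the first PCR after prophylaxis, with no negative PCR at or after the end of drug, as *onset undetermined*. Report breakthrough and late infection twice, with these cases assigned each way.
2. Report CMV infection at 3, 6 and 12 months split into scheduled and triggered detections, using the reason already captured. Alongside, give the number of patients who had had a scheduled PCR by each time, by serostatus, including D-/R-.
3. State whether the CMV row in the section 10.0 table means PCR or review of the record, and reconcile it with section 3.0 and item 10. State whether the R+ months run from transplant or from drug stop.

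The cost is some wording and a small additional tabulation from dates and reasons already collected, with no extra tests. The drawback is that some cases lose a definite label, and statements about breakthrough and late infection become less firm.

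### CMV infection and breakthrough infection use different viral-load thresholds, infections after an early stop are neither breakthrough nor late, and late disease is dated by first infection

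*Combined protocol and SAP*

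**What the plan says.** Section 4.0, Efficacy Measures, item 10 (CMV infection, a secondary outcome) makes these statements in one paragraph:

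- Infection is "defined as detectable CMV in the patient's plasma", and "The lower level of detection is 50 IU/mL".
- With a reference to the centre's own CMV protocol and an appendix, "any level >1,000 IU/mL will be considered CMV infection for the purposes of this study".
- For the late class: "Late CMV infection will be defined based on occurrence of first CMV infection after completion of CMV prophylaxis (3- or 6-months post-transplant".
- For the on-treatment class: "Breakthrough cases of CMV infection, defined as the presence of CMV DNA while on anti-CMV prophylaxis, will also be assessed".

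Item 11 (CMV disease, also secondary) requires organ dysfunction, CMV infection and biopsy proof together. It then says "Late CMV disease will be defined based on occurrence of first CMV infection after completion of CMV prophylaxis", with the same month 3 or 6 in parentheses. It ends "Breakthrough cases of CMV disease will also be assessed", and no definition of those cases follows.

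Three other places bear on this. Section 3.0 plans six months of prophylaxis for D+/R- patients and three months for everyone else. Section 4.0, item 5 makes reducing, holding or discontinuing either antiviral a secondary outcome of its own. Section 6.0 analyses by intent to treat and does not replace patients taken off study drug. The Statistical Methods in section 10.0 give no rule for assigning an infection or a disease episode to a class.

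**The concern.** One paragraph gives infection two thresholds and gives breakthrough infection none. Two people abstracting the same chart could therefore count different numbers of infections and of breakthrough cases. The same low-level PCR result would be a failure of prophylaxis while the patient takes the drug, and not an event once the course is finished.

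The time split has a second problem. Breakthrough needs the patient to be on drug, and late needs the course to be complete. The plan foresees holds and discontinuations, but gives no class to an infection that follows one before month 3 or 6.

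The third problem is the dating of disease. A reader would take late CMV disease to mean disease that arises after prophylaxis has ended. The rule looks instead at when infection was first recorded.

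At stake is how the secondary efficacy results can be read: whether failures happened on the drug, after it was stopped early, or after a full course. Section 10.0 describes the trial as open-label. If these choices are left until the data are reviewed, they will be made with treatment assignment known.

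**Working it through.** The plan gives no figure to reproduce here, so the check applies the definitions as written to example patients.

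**Inputs.** From item 10: detection limit 50 IU/mL; study threshold >1,000 IU/mL; breakthrough = any CMV DNA while on drug; late = first infection after completion at month 3 or 6. From section 3.0: planned course of 3 or 6 months. The viral loads and times in the examples are illustrative.

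**Threshold gap.** 1,000 / 50 = 20, and log10(20) = 1.30. Values from 50 to 1,000 IU/mL inclusive are detectable but below the study's bar.

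**Classification with >1,000 IU/mL as the infection rule:**

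| Example | Infection | Breakthrough | Late |
|---|---|---|---|
| 200 IU/mL, month 2, on drug | no | yes | no |
| 1,000 IU/mL, month 2, on drug | no | yes | no |
| 5,000 IU/mL, month 2, on drug | yes | yes | no |
| 5,000 IU/mL, month 2.5, stopped at month 1 of 3 | yes | no | no |
| 5,000 IU/mL, month 4, stopped at month 2 of 6 | yes | no | no |
| 5,000 IU/mL, month 8, stopped at month 2 of 6 | yes | no | depends |
| 5,000 IU/mL, month 8, completed 6 months | yes | no | yes |
| 200 IU/mL, month 8, completed 6 months | no | no | no |

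The first two rows show that breakthrough is not contained in infection. The first and last rows show the same viral load treated differently on and off drug. The fourth and fifth rows are infections that neither class takes. There the window without a class runs from the stop to the planned end: 3 - 1 = 2 months and 6 - 2 = 4 months. The sixth row is late if completion means the planned calendar month, and has no class if it means finishing the course.

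**Same examples with any detectable DNA as the infection rule.** The two low on-drug values become infections, so breakthrough is then a subset. The last row becomes a late infection. The early-stop rows do not change, so that gap does not depend on which threshold governs.

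**Disease.** Take a D+/R- patient with a plasma level above 1,000 IU/mL at month 2 on drug and biopsy-proven disease at month 8, after six months of prophylaxis. The first infection is at month 2, before completion, so item 11 does not call the disease late although it arose two months after the drug ended (8 - 6 = 2). Whether it is breakthrough disease cannot be decided, because item 11 does not define that class.

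**The case against.** The best defence of the threshold is to read the paragraph as a whole. Item 10 speaks of breakthrough cases of CMV infection, and it has already said what counts as CMV infection in this study. If that rule carries over, breakthrough is a subset and nothing conflicts. Breakthrough is also a subset if detectability governs throughout. This stands as a possible reading, but the breakthrough sentence supplies its own definition without a level and does not refer back. Item 10 also cites an appendix that is not in the public text. If the appendix fixes one threshold for all uses, a cross-reference would settle that part.

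On disease, the word *first* could mean the first infection recorded after the drug ended rather than the patient's first ever. Even so, the class would depend on the date of an infection and not on the onset of disease.

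Several stronger conclusions are tempting and are not supported:

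- *Infections after an early stop are lost.* They are not. Above 1,000 IU/mL they count in overall CMV infection at every later assessment. Only the breakthrough or late label is missing.
- *Aim 2 fails.* Hypothesis 2 concerns the overall incidence of infection and disease at 3, 6 and 12 months, not the breakthrough and late split. Section 10.0 already concedes limited power for CMV infection.
- *The arms can no longer be compared.* Each definition applies to both arms alike, and no section says that breakthrough and late must add up to the total.
- *Breakthrough cases will outnumber infections.* That is possible only under the mixed reading, and nothing in the documents shows that it would happen.
- *The gap falls on a known number of patients per arm.* The neutropenia rates in section 2.0 come from studies of CMV treatment. They are not rates of stopping prophylaxis, and the plan makes no prediction by arm of early stopping.
- *Item 11 is wrong to require CMV infection for disease.* That is a coherent composite definition, and changing it would be a preference.

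**Conclusion.** The definitions need correcting before analysis, on three counts. First, item 10 states infection at two levels 20-fold apart and gives breakthrough infection no level, so with >1,000 IU/mL as the operative rule breakthrough is not a subset of infection. This rests on reading the breakthrough sentence literally. Second, an infection after an early stop or during a hold, before the planned end, is neither breakthrough nor late. This holds under either threshold, provided that completion is not stretched to mean any end of prophylaxis; the stated months argue against that. Third, late disease is dated by first infection and breakthrough disease is undefined. With *first* taken as the patient's first infection, disease arising after prophylaxis is not late if infection was recorded earlier.

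The effect is confined to secondary endpoints and their sub-classes. The primary leukopenia outcome and the sample size do not depend on any of these definitions. The number of patients affected cannot be computed, because the documents give neither a rate of low-level viremia on prophylaxis nor a rate of early discontinuation.

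**What to change.** Amend items 10 and 11, and repeat the rules in the Statistical Methods:

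1. Use the study's own threshold, >1,000 IU/mL, for infection, breakthrough infection and late infection. Report detectable DNA at 50 to 1,000 IU/mL on a separate line as viremia.
2. Classify each patient's first infection by actual drug status on that date: on drug (breakthrough); off drug before the planned end, whether stopped or held; after the planned end (late). State how a patient who stopped early and is infected after the planned end is classified.
3. Date CMV disease by its own onset, and define late and breakthrough disease from drug status at that onset.

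The change is to wording only. Section 10.0 already has laboratory data, antiviral doses and biopsy reports abstracted from the record, so no visit, test or treatment changes. The downside is a lower breakthrough count, because on-drug values of 50 to 1,000 IU/mL move to the viremia line, where they stay visible.
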